### *3. Severity of myelopathy*

The Modified Japanese Orthopaedic Association score for severity of myelopathy will be used to determine the severity of myelopathy i.e.

Mild (Modified Japanese Association Score - MJOA)  $\geq 15$

Moderate (MJOA = 12)

Severe (MJOA < 12).

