### Hypothesis

We hypothesise that decreased HRV is common in patients undergoing surgery for cervical myelopathy and that decreased HRV is a predictor of hypotension on induction of general anaesthesia. We also hypothesise that there is a relationship between severity of myelopathy and degree of abnormalities in HRV.

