## Data Collection and Management

### Data Collection

The following data will be collected: patient demographics, surgical data including position technique, number of levels, duration, anaesthetic data including agents used, hemodynamic measurements from preinduction to surgical incision, Japanese Orthopaedic Association Score. The incidence of hypotension and the number of interventions required to keep mean arterial blood pressure above 70 mmHg will be recorded.

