## Analysis

The incidence of low HRV as indicated by a total power below the normal range of  $3466 \text{ ms}^2 \pm 1018 \text{ ms}^2$  will be determined as well as the incidence of hypotension. We will determine the correlation between low HRV, hypotension and the severity of myelopathy as determined by the Japanese Orthopaedic Association score. Non-parametric HRV within group data will be analysed with the Wilcoxon matched pairs test. Comparisons of non-parametric HRV data between groups will be performed using the Mann–Whitney test. Student t test will be used for parametric data.

Definitions:

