### Sample size

There is only one previous study that has looked at the autonomic dysfunction in patients with cervical myelopathy. They had a sample size of 30 patients and majority of patients had either moderate or severe myelopathy. Currently there is no data on the incidence of low HRV in patients with varying severities of cervical myelopathy. We plan to recruit around 100 patients with various degrees of cervical myelopathy for this study. Around 25 % of patients will be mild to moderate myelopathy and rest will be moderate to severe. Hence this sample size will provide us the useful information on the true incidence of autonomic dysfunction across different severities of myelopathy.

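### The printed mJOA severity bands leave scores 13 and 14 without a class, which affects only results reported by severity band

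*Combined protocol and SAP*

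**What the plan says.** Item 3 of the definitions (Severity of myelopathy) makes the modified Japanese Orthopaedic Association (mJOA) score the measure of severity and prints three bands:

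- "Mild (Modified Japanese Association Score - MJOA") with a limit of 15 or more
- "Moderate (MJOA = 12")
- "Severe (MJOA < 12")

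Severity is used in three other places:

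- **Hypothesis:** the study expects that "there is a relationship between severity of myelopathy and degree of abnormalities in HRV".
- **Analysis:** "We will determine the correlation between low HRV, hypotension and the severity of myelopathy as determined by the Japanese Orthopaedic Association score". The text does not say whether this means the numeric score or the bands.
- **Sample size:** recruiting around 100 patients is justified by information on "the true incidence of autonomic dysfunction across different severities of myelopathy". The expected mix is given as "Around 25 % of patients will be mild to moderate myelopathy and rest will be moderate to severe".

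The score itself is on the list under Data Collection.

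**The concern.** A set of severity classes should place every possible score in exactly one class. Here the middle class is one value, and there is a gap between it and the mild class. No other section says where 13 and 14 go or how an unclassified patient is handled.

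Anyone following the printed rule would leave these patients out of every by-band result. Otherwise the analyst would have to place them by a decision made after the data are in hand. The by-band incidence of low HRV is what the Sample size section offers as the study's yield, and severity is part of a stated hypothesis, so the classes should be usable as written. If the correlation in the Analysis section is meant to use the bands, it inherits the same gap.

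**Working it through.** **Step 1. Apply the printed bands to each score.** The protocol gives no score range, so whole numbers from 0 to 18 are assumed.

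| mJOA score | Class as printed |
|---|---|
| 0 to 11 | severe |
| 12 | moderate |
| 13, 14 | none |
| 15 to 18 | mild |

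No score falls in two classes, and 13 and 14 are the only ones in none. The gap does not depend on the assumed end points of the scale.

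**Step 2. Find the fills that fit.** Severe ends at 11 and mild starts at 15. If both limits stand and three bands are kept, moderate must be 12 to 14. Placing 13 or 14 in mild or severe would contradict a printed limit.

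**Step 3. Trace which results use the bands.**

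| Result | Uses the mJOA bands? |
|---|---|
| Low versus normal HRV groups (total power) | No |
| Hypotension groups (arterial pressure and interventions) | No |
| HRV-hypotension link | No |
| Correlation with severity | Only if severity means the bands; not stated |
| Incidence across severities | Yes, if reported by band |

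**Step 4. Illustrate the size.** The protocol gives no mJOA distribution and derives its sample size from no formula, so there is no stated figure to reproduce. As an illustration, take a normal distribution with mean m and SD s, cut into whole scores:

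P(score = k) = [Φ((k + 0.5 − m)/s) − Φ((k − 0.5 − m)/s)] / total over k = 0 to 18

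The SD was set at 2, 2.5 and 3 and the mean at 9 to 14. Scenarios with more than 25% of patients at 15 or above were left out, because the Sample size section puts mild to moderate at about 25%, so mild alone should not exceed that. This drops mean 13 with SD 2.5 (0.264) and SD 3 (0.285), and all of mean 14 (0.393 to 0.399).

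P(13 or 14) in the scenarios kept:

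| Mean | SD 2 | SD 2.5 | SD 3 |
|---|---|---|---|
| 9 | 0.037 | 0.067 | 0.088 |
| 10 | 0.093 | 0.123 | 0.136 |
| 11 | 0.187 | 0.194 | 0.188 |
| 12 | 0.296 | 0.263 | 0.235 |
| 13 | 0.373 | dropped | dropped |

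The range is about 4 to 37 of 100 patients. As a share of those scoring 12 to 14, the unclassified run from 0.361 (mean 9, SD 2) to 0.681 (mean 13, SD 2).

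Worked case, mean 12 and SD 2:

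- P(13 or 14) = Φ(1.25) − Φ(0.25) = 0.894 − 0.599, which is 0.296 after rescaling to 0 to 18.
- P(12) = 0.198, P(12 to 14) = 0.493 and P(15 or more) = 0.105.
- The unclassified share of the natural moderate group is 0.296/0.493 = 0.60.

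**Step 5. Test a stricter reading of the case mix.** If the 25% covers everyone scoring 12 or more, only mean 9 (all three SDs) and mean 10 with SD 2 remain. The unclassified share is then 0.037 to 0.093, or about 4 to 9 of 100. The worked case above fails this reading, since about 60% of its patients score 12 or more.

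**The case against.** Four arguments can be made against the point.

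*It may be a conversion fault.* A severity band of one value is an unlikely intention. An upper limit may have dropped out, or an at-least sign may have been read as an equals sign; either would close the gap. A lost character usually leaves no trace, so the absence of a visible gap in the text proves little. This stands as a caution: confidence is high about the text as printed, not about what the authors meant. It is why the source check comes first.

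*No specified analysis is shown to need the bands.* The Analysis section refers to severity as determined by the score, and a numeric correlation is a natural reading. This stands in part. That correlation may well be unaffected, but the protocol does define bands and does promise information across severities, so some reporting by band is to be expected.

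*The repair is obvious.* It is, and an analyst would probably use 12 to 14. That limits the importance of the point but does not make the printed rule workable.

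*The size is mostly assumption.* Shape, mean, SD and scale are all assumed, the range is about ninefold, and the case-mix sentence names moderate on both sides of its split, so its meaning is unclear. This stands. The figures only illustrate what the gap could amount to, and the defect does not rest on them.

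**Conclusion.** The concern holds for the text as printed: scores 13 and 14 have no severity class, and no other section supplies one. The effect is confined to results by severity band, and it reaches the severity correlation only if that uses the bands. The study's other main results keep all patients.

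The number affected cannot be known from the protocol. About 4 to 37 of 100 follows from an assumed normal distribution on a 0 to 18 scale with mean 9 to 13, SD 2 to 3 and no more than 25% mild; the stricter case-mix reading narrows this to about 4 to 9 of 100. Because only one fill agrees with both printed limits, the room for an arbitrary choice is small, and the point is minor.

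**What to change.** - Check the source file for a lost limit or altered symbol in the moderate line. If it already reads 12 to 14, the band question is closed and only the third item below remains.
- Otherwise state moderate as mJOA 12 to 14. With severe below 12 and mild at 15 or more, this leaves no gap and no overlap.
- In the Analysis section, say that the severity correlation uses the numeric mJOA total, for example as a rank correlation, and that the bands are for description. This is not needed to close the gap, but it removes the ambiguity about which form of severity is analysed.
- As tidying only, use the name of the modified score in the Data Collection and Analysis sections, as the definition does.

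The cost is a wording change made before analysis. The score is already to be collected, so no further data or patients are needed.

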### Sample size

There is only one previous study that has looked at the autonomic dysfunction in patients with cervical myelopathy. They had a sample size of 30 patients and majority of patients had either moderate or severe myelopathy. Currently there is no data on the incidence of low HRV in patients with varying severities of cervical myelopathy. We plan to recruit around 100 patients with various degrees of cervical myelopathy for this study. Around 25 % of patients will be mild to moderate myelopathy and rest will be moderate to severe. Hence this sample size will provide us the useful information on the true incidence of autonomic dysfunction across different severities of myelopathy.

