## Background

Cervical myelopathy is commonly associated with degenerative spinal disease. It is a common cause of spinal cord dysfunction in the aging population. The predominant pathology seen in these patients is spondylosis which includes degeneration of joints, discs and ligaments. (1). Spinal cord ischemia may also contribute to these pathological processes but the exact mechanism remains unclear. Magnetic resonance imaging may reveal disc herniation, osteophytic narrowing of the spinal canal and hypertrophic changes to the ligamentum flavum (2). Patients may present with a wide range of symptoms ranging from neck pain and decreases in dexterity in mild cases to sphincter dysfunction and complete loss of motor function in severe cases (3). Dysfunction of the autonomic nervous system is also evident in many cases of cervical myelopathy (4). In many of these patients, the spinal cord is at risk of ischemia due to decreased blood flow as a result of compressive lesions. Any further reduction in spinal cord blood flow may not be well tolerated. Mean arterial pressure (MAP) is one of the important factors that determine the adequacy of perfusion to the spinal cord and hypotension has been shown to be associated with poor outcome in patients with spinal cord injury.

Autonomic nervous system dysfunction is often seen in patients with acute spinal cord injury. (5). A recent study has shown autonomic nervous system involvement in up to 50% of patients with compressive cervical myelopathy (4). The autonomic nervous system (ANS) is responsible for the normal regulation of visceral organ function including the cardiovascular system. They are the primary regulator of heart rate and blood pressure.

Surgical treatment of cervical myelopathy may involve anterior and/or posterior decompression of spinal cord with or without instrumented fusion. The main purpose of the surgery is to prevent further deterioration of spinal cord function. Patients with cervical myelopathy often pose a significant challenge to the anesthesiologists. In addition to challenges with airway management and patient positioning, the most important anesthetic consideration in these patients is to maintain the mean arterial blood pressure (MAP) >70 mmHg during the surgery.

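### The hypothesis concerns the degree of HRV abnormality by severity, but the named correlation uses low HRV as a yes/no variable and loses roughly a third to a half of the information

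*Combined protocol and SAP*

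**What the plan says.** The Hypothesis section states that "there is a relationship between severity of myelopathy and degree of abnormalities in HRV". The Analysis section says: "We will determine the correlation between low HRV, hypotension and the severity of myelopathy", with severity determined by the Japanese Orthopaedic Association score. It names no coefficient. The heart rate variability definition forms the low and normal groups by placing total power below or within a stated normal range. The severity definition bands the modified score into mild, moderate and severe.

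The Analysis section also plans Mann–Whitney or t tests of HRV data between groups, without saying which groups.

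The Sample size section says: "We plan to recruit around 100 patients with various degrees of cervical myelopathy for this study". It gives the expected mix: "Around 25 % of patients will be mild to moderate myelopathy and rest will be moderate to severe". It acknowledges that "Currently there is no data on the incidence of low HRV in patients with varying severities of cervical myelopathy" and ends: "Hence this sample size will provide us the useful information on the true incidence of autonomic dysfunction across different severities of myelopathy". It states no precision target, assumed incidence, significance level or power.

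**The concern.** The hypothesis is about a graded quantity. The only analysis that links HRV to severity by name replaces total power with a two-level variable, and it may also replace the severity score with three classes. Each cut discards information that the study collects anyway. With about 100 patients this matters: a real but modest relationship could easily be missed, and a null result could then be taken as evidence of no relationship.

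A smaller concern lies in the Sample size section. It speaks of incidence across severities without saying how precise that incidence will be. Moderate myelopathy also falls in both planning strata, so the expected number in each severity class cannot be worked out.

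**Working it through.** **Inputs from the documents.** N is about 100, with about 25 in the milder stratum and about 75 in the other (Sample size). The only rate given is in the Background: "A recent study has shown autonomic nervous system involvement in up to 50% of patients with compressive cervical myelopathy". It is used here as 50% low HRV, although it describes autonomic involvement rather than low total power.

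**Assumptions.** Severity score and total power (suitably transformed) are bivariate normal, and tests are two-sided at 0.05. Where three classes are used, the split is 25/40/35, because the documents do not give one.

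**The plan's own figure.** There is no calculation behind 100 to reproduce. For reference, ±10 points at 50% incidence needs n = 1.96² × 0.25 / 0.10² = 96.04, so 97. The plan states no such target.

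**Information kept after cutting total power.** For a cut that puts a share p in one group, the fraction kept is φ(z_p)² / [p(1 − p)].
- At p = 0.50: 0.3989² / 0.25 = 0.64.
- This is the most favourable cut. At p = 0.16 the same formula gives 0.44.

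**Information kept after banding severity.** The fraction is Σ p_k m_k², where m_k is the mean of a standard normal within class k. For 25/40/35 the means are −1.27, −0.13 and 1.06, so 0.25 × 1.616 + 0.40 × 0.017 + 0.35 × 1.120 = 0.80.

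**Joint effect.** Raw score with binary HRV keeps 0.64. Three classes with binary HRV keep 0.80 × 0.64 = 0.51.

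**Reference correlation.** With 100 patients, a continuous (Pearson) analysis has 80% power for r = tanh[(1.96 + 0.84) / √97] = 0.277, so r = 0.28 is used below.

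**Power at r = 0.28.** By Fisher's z, power is Φ[atanh(r√e) × √97 − 1.96], where e is the fraction kept. Simulated values are shown beside it.

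| Analysis | e | r√e | Fisher z | Simulated |
|---|---|---|---|---|
| Both continuous | 1 | 0.28 | 81% | Pearson 80%, Spearman about 75% |
| Raw score, low/normal HRV | 0.64 | 0.22 | 61% | 58% (rank test) |
| Three classes, low/normal HRV | 0.51 | 0.20 | 51% | about 51% |

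The Spearman and rank-test figures are the fair comparison, because total power is likely to be skewed and the score is ordinal. At r = 0.20, Spearman has 49% power against 36% for the raw score with binary HRV. At r = 0.40 the figures are 98% and 90%.

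**Precision of incidence.** The 95% half-width is 1.96 × √[p(1 − p)/n], in percentage points.

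| n | p = 50% | p = 20% | p = 10% |
|---|---|---|---|
| 100 | 9.8 | 7.8 | 5.9 |
| 75 | 11.3 | 9.1 | 6.8 |
| 25 | 19.6 | 15.7 | 11.8 |

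At 12 of 25, the exact interval is 27.8% to 68.7%.

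**The case against.** The plan is not wholly categorical. Its reference to the Japanese Orthopaedic Association score may mean the score itself. The Mann–Whitney and t tests of HRV data use undivided values, and total power is measured as a value. This stands in part: a graded analysis is not excluded. But the groups for those tests are not named, a two-group test does not by itself cover three severity classes, and the one analysis tied to severity uses low HRV.

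A reader might go further and take the 25/75 mix as an analysis cut. Against low/normal HRV, that would keep only about 35% of the information, with 38% power at r = 0.28. The documents do not support this: the mix is an expected recruitment pattern, the severity definition has three classes, and no comparison of 25 with 75 patients is planned.

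A reader might also infer that the Sample size section makes a claim the study fails to meet. It promises useful information, sets no precision target, and is planning a first description where no data exist. Precision in the 75 is close to that overall; only the milder stratum is markedly imprecise, and less so if incidence is below 50%.

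Finally, continuous analysis helps mainly with the association. For incidence in the mildest quarter, a logistic model (assumed r = 0.3) narrows the half-width only from about 19 to about 15 points. That objection stands, so incidence by severity should remain descriptive.

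**Conclusion.** The point holds as a mismatch between hypothesis and analysis. Using low HRV in place of total power keeps about 64% of the information if severity is the raw score, and about 51% if it is three classes. At a true correlation of 0.28 this costs about 17 to 24 percentage points of power (75% down to 58% or 51%). The sizes rest on assumed normality, 50% low HRV and, for the lower figure, the assumed 25/40/35 split. They would shift with a skewed or heavily tied score, but the direction would not.

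The Sample size wording is secondary: it needs expected widths and distinct strata. The printed definition "Moderate (MJOA = 12" leaves scores 13 and 14 without a class, but this may be a fault of text extraction and nothing here depends on it. The overlap of moderate between the two planning strata stands without it.

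**What to change.** **Analysis section.** Name the severity analysis as a Spearman correlation of total power with the modified Japanese Orthopaedic Association score in all patients, or a linear regression of log total power on that score. Report the estimate with a 95% confidence interval. Keep the low/normal HRV groups and the severity classes for descriptive incidence, with exact intervals.

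**Sample size section (secondary).** Say that overall incidence will be known to about ±10 points and that incidence by severity is descriptive: at 50% incidence, about ±11 points in 75 patients and ±20 in 25, narrower at lower incidence. Replace the two overlapping strata with non-overlapping ones that match the severity definition, and give expected numbers in each.

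**Cost.** Wording only. Total power and the score are already collected and no more patients are needed. The statement about incidence across severities becomes more modest.

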### Ethical Aspects

#### Regulatory approval

Regulatory approval will be sought from the local research ethics board and the study will not commence until it is obtained.

#### Informed Consent

Prior to enrolment potential participants will receive written and verbal information regarding the nature and purpose of the study, what participation involves and potential benefit and risks. They will be given time to ask questions and it will be emphasized that participation is voluntary, that they are free to withdraw from the study at any time and that any decision to do so will not affect any treatment they would otherwise receive. Where the participant understands and accepts these terms, they will be asked to sign the consent form.

**Privacy and Confidentiality**

The laptop used in the study will contain only de-identified data and that it will be encrypted as per UHN policy 1.40.006 Storage, Transport & Destruction of Confidential Information.
